4.1 Inclusion Criteria

- Patients must be diagnosed with at least one of the following: trigger finger, de quervain's tenosynovitis, or tennis elbow (lateral epicondylitis)
- Subjects may be treated for multiple sites of pathology simultaneously or sequentially and up to three sites of pathology can receive an injection during an office visit
- Subjects may have a maximum total of two injections at each site of pathology during the study
- Age 18 years of age or older from all racial/ethnic types
- · Both males and females
- Study participants will not receive splinting as a therapeutic addition to their treatment.
- Study participants will include any NYU employee or students as these individuals also can get hand and upper extremity pathology. It will be specifically reiterated to them that their academic status or grades, or employment will not be affected by their decision to participate in this study. Record of the participation cannot be linked to an academic record.

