1.1 Background

Many orthopaedic hand disorders are comprised of different forms of tendonitis, tenosynovitis, and arthritis. The inflammatory processes of these disorders cause discomfort and functional impairment for patients. Decreasing the inflammatory response by use of splinting, physiotherapy, systemic anti-inflammatory agents, and local anti-inflammatory injections helps to alleviate some or all of the discomfort (2-4). Steroid injections are not entirely benign, and complications include tendon ruptures, subcutaneous fat atrophy, skin pigmentation changes, cartilage damage, and hyperglycemic responses in diabetics (9-11, 22-23). Studies have shown that ketorolac, a non-steroidal anti-inflammatory agent has a potent anti-inflammatory effect comparable to corticosteroids and a strong analgesic effect allowing for reduced opioid consumption postoperatively (7, 8). One could argue that the potent anti-inflammatory properties of ketorolac could be used to substitute for local corticosteroid injections in treating certain hand disorders. Given the side-effect profile for corticosteroids it may be beneficial to treat inflammatory disorders with local ketorolac injections. Nonsteroidal anti-inflammatory agents also have their known systemic adverse effects including gastric ulceration and intestinal bleeding as well as impairment of renal function. Most of these side effects are theoretically avoided with local tissue injections.

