1.6 Research Risks & Benefits

1.6.1 Risk of Study Drug

All patients will be monitored closely as per the data and safety monitoring plan established for this project for any side-effects that may arise from using these medications for local soft tissue infections. Patients will be checked for common side effects at the time of their follow-up visits. In addition, the patient will be given instructions to contact the private office/HJD hand clinic to report any potential side effects that they may be experiencing.

Risks associated with dexamethasone injections include (9-11, 22-23):

- Pain/discomfort at the site of injection
- Tendon ruptures
- Subcutaneous fat atrophy
- Skin pigmentation changes
- Cartilage damage
- Hyperglycemic responses in diabetic patients

Risks associated with Ketorolac in the literature refer mainly to systemic or intramuscular administration and no risks are noted for local soft tissue injections. Ketorolac has been shown to cause (28-29):

- Pain/discomfort at the site of injection
- Increased risk for bleeding
- Skin rashes
- Pruritis
- Allergic reactions such as face/throat swelling
- Abdominal pain/GI upset
- Gastrointestinal ulcers/GI bleeding
- Renal impairment

Risks associated with lidocaine mainly involve side-effects from systemic administration which include (30,31):

- CNS depression or excitation (light-headedness, nervousness, apprehension, euphoria, confusion, dizziness, drowsiness, tinnitus, blurred vision, vomiting, twitching, convulsions, unconsciousness, respiratory depression and arrest)
- Bradycardia
- Hypotension
- Cardiovascular collapse
- Allergic reactions

Protection against risks

Patients will be injected using sterile technique to avoid any infectious risk with the medication. Patient will be informed that some discomfort will be experienced with needle injection however small gauge needles will be used to minimize the pain felt by the patient. Any patient that experiences an adverse event will be withdrawn from the study and will follow-up with their primary care provider promptly.

Payment for the office visit and any procedures performed will be billed to the insurance company of the patient and the patient is responsible for any copayments needed.

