4.2 Exclusion Criteria

- Patients had previous steroid injection at the site in question within 90 days of enrollment
- Patients with a history of gastric ulcers, renal impairment, allergy/hypersensitivity to non-steroidal anti-inflammatory (NSAID) or lidocaine derivative medications, immunocompromised patients (HIV/AIDs) and pregnant females

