5.1.1 Description

Ketorolac is a nonsteroidal anti-inflammatory drug (NSAID). The approved indication for Ketorolac is for the short-term (≤5 days) management of moderately severe, acute pain that requires analgesia at the opioid level, usually in a postoperative setting. It is highly protein bound (99%) and is largely metabolized by the liver. It is indicated for short-term management of severe acute pain as intravenous or intramuscular injections.

In its approved indication it is contraindicated for those with renal impairment, active peptic ulcer disease, pregnant or nursing females, individuals with NSAID hypersensitivity, or individuals at high risk for bleeding/clotting disorders.

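### Section 4.2 omits, without giving a reason, two of the six groups that 5.1.1 lists as contraindicated for ketorolac in its approved indication: nursing women and people at high bleeding or clotting risk

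*Combined protocol and SAP*

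**What the plan says.** Section 5.1.1 of the protocol, repeating 1.2, lists the contraindications of ketorolac in its approved indication. They are renal impairment, active peptic ulcer disease, and "pregnant or nursing females, individuals with NSAID hypersensitivity, or individuals at high risk for bleeding/clotting disorders". Both 1.2 and 5.1.2 say that the use in this trial lies outside that indication.

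Section 4.2 opens its list of medical exclusions with "Patients with a history of gastric ulcers, renal impairment", goes on to NSAID or lidocaine hypersensitivity, and closes with "immunocompromised patients (HIV/AIDs) and pregnant females". Its only other criterion concerns a recent steroid injection at the same site. Neither nursing nor bleeding or clotting risk appears there.

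On risk, 1.6.1 includes "Increased risk for bleeding" among the effects of ketorolac. It qualifies the list by saying that the reported risks "refer mainly to systemic or intramuscular administration and no risks are noted for local soft tissue injections". Section 1.1, after naming gastric, intestinal-bleeding and renal effects of NSAIDs, adds: "Most of these side effects are theoretically avoided with local tissue injections". Section 5.7 allows any oral medication alongside the study injections.

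On exposure, 4.1 states that "up to three sites of pathology can receive an injection during an office visit". Section 5.1.2 fixes each ketorolac injection at 1 mL of 30 mg/mL, and 5.5 gives a patient the same drug at every site.

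**The concern.** The protocol names the groups for whom the drug's labelled use is contraindicated and then turns most, but not all, of that list into exclusion criteria. A nursing woman, or a patient with a clotting disorder, can meet every criterion in 4.1 and 4.2, be enrolled, and be assigned ketorolac.

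For the second group the gap touches a risk that the protocol itself records, since 1.6.1 lists bleeding. Because 5.7 sets no limit on oral medication, nothing else in the eligibility or concomitant-therapy rules would screen these patients out. Clinical discretion is a weak substitute. A physician may decline to enrol someone, but nothing written requires it, and after enrolment the treating physician is blinded (5.6, 5.8) and cannot steer such a patient away from ketorolac.

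What is at stake is participant safety. The treatment comparison is not affected: eligibility is settled before assignment, so the omission favours neither arm.

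**Working it through.** **Step 1: the two lists side by side.** The left column is from 5.1.1 (the same list is in 1.2), the right column from 4.2.

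| Contraindicated in the approved indication (5.1.1) | Counterpart in 4.2 |
|---|---|
| Renal impairment | Renal impairment |
| Active peptic ulcer disease | Past gastric ulcers (approximate) |
| Pregnant | Pregnant |
| Nursing | None |
| NSAID hypersensitivity | NSAID allergy or hypersensitivity |
| High bleeding or clotting risk | None |

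Six groups are listed, four have a counterpart, and 6 - 4 = 2 have none. The ulcer match is imperfect: a past gastric ulcer is wider in time but does not name non-gastric peptic ulcers. I have counted it as covered, which is the reading more favourable to the plan.

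**Step 2: is a reason given?** The only passages that could supply one are 1.1 and 1.6.1, which argue that local injection largely avoids systemic effects. That argument is general. It is not tied to nursing or to bleeding risk, and no section says that these two groups were considered and admitted on purpose. The same argument would apply at least as well to renal impairment and gastric ulceration, both of which 1.1 discusses as systemic NSAID effects and both of which 4.2 still excludes.

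**Step 3: the exposure these patients could receive.**

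- Dose per injection (5.1.2): 1 mL x 30 mg/mL = 30 mg. As a check on the arithmetic, 0.5 mL of 1% lidocaine is 0.5 x 10 mg/mL = 5 mg, which agrees with the protocol's figure.
- Sites per visit (4.1): up to 3.
- Same drug at each site (5.5).
- Maximum ketorolac at one visit: 3 x 30 = 90 mg.

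Section 1.5 argues for the 30 mg/mL concentration and does not state a per-visit total. The one human dose it cites is 60 mg in a shoulder trial, and 90 / 60 = 1.5.

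**Step 4: how many patients?** The documents give no figure for the share of candidates who are nursing or at high bleeding or clotting risk, so no headcount can be derived.

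**The case against.** The strongest reply is that 5.1.1 describes the approved indication, while this trial gives a local peritendinous injection outside it. The protocol never says that these two groups are contraindicated for that use. It says that most systemic effects should be avoided, and keeping some labelled contraindications while dropping others could be a deliberate choice. There is also human experience of local ketorolac: 1.4 reports a double-blind subacromial trial, so the statement in 1.3 that no published studies exist applies only to hand pathology.

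Much of this stands. The documents cannot show whether the omission was an oversight or a decision, and I do not claim that the protocol contradicts itself. It does not remove the point, however. A deliberate selection needs a stated reason, and none is given for applying four groups to this use and dropping two. The account of the shoulder trial in 1.4 reports nothing about either group.

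A reader might go further in three ways that the documents do not support:

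- *That 90 mg is an overdose, or that 60 mg is a ceiling.* No maximum dose is given anywhere in the text. The 60 mg is a precedent from one study, and the 90 mg follows openly from 4.1, 5.1.2 and 5.5.
- *That the protocol hides repeat dosing by describing a single administration.* Section 4.1 settles this: "Subjects may have a maximum total of two injections at each site of pathology during the study". Section 5.1.2 likewise allows one repeat per site.
- *That oral anticoagulants or oral NSAIDs are themselves contraindicated.* Section 5.1.1 does not list them. Section 5.7 matters only because it adds no screen for bleeding risk.

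**Conclusion.** The concern holds as a gap in the eligibility criteria. Two of the six groups listed in 1.2 and 5.1.1 as contraindicated for ketorolac in its approved indication are missing from 4.2 without explanation, and as written such patients can be randomized to ketorolac at up to 90 mg per visit. Harm to either group from local injection is not demonstrated, and the number affected is unknown.

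The conclusion rests on two things. The first is counting the ulcer criterion as covered; a stricter reading would add a partial third gap. The second is the text available: 8.4 and 10.1 refer to an attached Data and Safety Monitoring Plan that is not included. A dose rule there could not be checked, but eligibility belongs in 4.2 in any case.

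The change should be made because it protects participants at little cost. It does not bear on the validity of the primary comparison.

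**What to change.** Add both groups to 4.2, in the terms of 5.1.1: nursing women, and people at high risk of bleeding or clotting disorders. Apply the criteria at screening, before the randomization envelope is opened, so that they act equally on both arms and leave the blind intact. If the sponsor prefers to admit either group, 4.2 should instead state the reason.

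The cost is two added criteria and the loss of some candidates, whose number the documents do not give. Someone must also decide what counts as high risk; a sentence saying whether current oral anticoagulant use qualifies would make screening consistent. No injection, visit, sample-size target or analysis changes.

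Optionally, 1.5 could state that three sites amount to 90 mg at one visit. That is a clarification only; no lower cap and no change to the three-site limit is asked for.

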4.2 Exclusion Criteria

- Patients had previous steroid injection at the site in question within 90 days of enrollment
- Patients with a history of gastric ulcers, renal impairment, allergy/hypersensitivity to non-steroidal anti-inflammatory (NSAID) or lidocaine derivative medications, immunocompromised patients (HIV/AIDs) and pregnant females

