5.2 Dexamethasone (Standard of care comparator)

5.2.1 Description

Dexamethasone is a synthetic corticosteroid and possesses glucocorticoid activity. It is indicated for intraarticular or soft tissue injection for: synovitis of osteoarthritis, epicondylitis, acute nonspecific tenosynovitis.

In its approved indication there use limitations for immunocompromised individuals, pregnant females, persons with allergy to steroids, individuals with systemic fungal infections, and individuals with cerebral malaria. It is contra-indicated in systemic fungal infections, and hypersensitivity to any component of this product, including sulfites.

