5.2.2 Treatment regimen

Dexamethasone will be used within its labeled indication for this study: intra-articular or soft tissue injection for: synovitis of osteoarthritis, epicondylitis, acute nonspecific tenosynovitis. It is the active comparator in this study.

Dexamethasone will be administered as a peritendonous soft tissue injection of 1 mL of dexamethasone sodium phosphate (4mg/mL) and 0.5 mL (5mg) of 1% lidocaine

Patients will be followed at the initial office visit, 4-weeks, 8-weeks, 12-weeks, and 6 months post injection to determine clinical response. A second injection can be given only once if the patient desires due to no clinical response at the 4 or 8-week follow-up.

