5.5 Method for Assigning Subjects to Treatment Groups

When a patient is enrolled and consented into the study a random envelope (labeled with an identification number) will be opened and in it will contain the group that the patient is randomized to: steroid or ketorolac. Envelopes are made using a randomization software that chooses one of the two drugs at random. When a patient is being enrolled in the study for an additional site of pathology, they will receive the same drug to which they were initially randomized at each site of pathology and a separate identifier number will be used to track the progress of each site.

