5.8 Blinding of Study Drug

The study will be a double-blinded prospective randomized controlled trial. Drugs will be stored in the local clinic/office medication storage room. When a patient is enrolled and consented into the study a random envelop (labeled with an identification number) will be opened and in it will contain the group that the patient is randomized to: steroid or ketorolac. On the date of the planned injection a nurse, resident, fellow or research assistant present at the site and not directly involved in the patient's care will draw up the medication and hand it to the physician who will administer the drug. Both the patient and the treating physician are blinded to the identity of the medication. Patient data will be recorded and kept in the envelope and only the hand department research assistant or the resident in charge of this project (who will not be directly involved in patient care) will know the identity of the treatment given to the enrolled patients. Because both liquids are clear the contents of the syringes do not need to be covered

6 Study Procedures

A specific patient population with hand and upper extremity pathologies will be studied including trigger finger, De Quervain's tenosynovitis, and lateral elbow epicondylitis. Patients with trigger finger will be diagnosed clinically by observing symptoms of catching or triggering of the digit with range of motion and tenderness localized to the A1 pulley. Patients with De Quervain's tenosynovitis will be identified clinically as having pain/tenderness at the first dorsal extensor compartment combined with a positive Finkelstein test (pain during full thumb adduction with ulnar deviation of the wrist). Patients with tennis elbow (lateral epicondylitis) will be defined as having lateral elbow pain/tenderness over the extensor origin and/or pain at the lateral epicondyle with resisted wrist extension.

Patients will be consented at the time of their visit with the hand surgeon. Based on inclusion/exclusion criteria it will be determined whether or not to enroll the patient in the study. Consent will be performed by discussing the study with the patient in the privacy of the exam room and having them sign the written consent form that will be IRB approved. There is no payment to the patient for participation and they will be charged for their normal office visit for treatment rendered.

7 Statistical Plan

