7.1 Sample Size Determination

The sample size as stated above was derived by a power analysis. A power analysis indicated that a total sample size of 200 patients randomized equally (1:1 randomization) to each treatment arm (i.e trigger finger, De Quervain's disease, and tennis elbow) without any blocking or stratification would provide 80% statistical power (alpha=.05, beta=0.20) to detect a 10% difference in mean DASH scores between cohorts assuming a common standard deviation of 25% (effect size = 10/25 = 0.4). To account for an estimated 30% loss to follow-up, we plan to enroll a total of 260 patients per treatment arm (i.e. trigger finger, De Quervain's disease, and tennis elbow). In total, there will be approximately 780 patients enrolled among all treatment arms, however we expect the trigger finger group to be the treatment arm that most rapidly enrolls patients.

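### Section 4.2 excludes neither of the two contraindications that the protocol itself states for dexamethasone, although any enrolled patient may be randomised to it

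*Combined protocol and SAP*

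**What the plan says.** Sections 1.2 and 5.2.1 state the same two contraindications for dexamethasone: "It is contra-indicated in systemic fungal infections, and hypersensitivity to any component of this product, including sulfites". Section 5.2.1 also lists "use limitations for immunocompromised individuals, pregnant females, persons with allergy to steroids, individuals with systemic fungal infections, and individuals with cerebral malaria".

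Section 4.2 has two bullets. The first excludes a steroid injection at the affected site in the 90 days before enrolment. The second reads: "Patients with a history of gastric ulcers, renal impairment, allergy/hypersensitivity to non-steroidal anti-inflammatory (NSAID) or lidocaine derivative medications, immunocompromised patients (HIV/AIDs) and pregnant females".

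On how these criteria are used, Section 6 says: "Based on inclusion/exclusion criteria it will be determined whether or not to enroll the patient in the study". Section 5.5 describes the step after consent: "Envelopes are made using a randomization software that chooses one of the two drugs at random". Section 5.1.2 confirms that dexamethasone is one of the two randomised groups. Sections 5.6 and 5.8 say that a person outside the patient's direct care draws up the syringe and that the treating physician does not know its content.

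**The concern.** In a two-drug randomised trial, every patient who passes screening should be able to receive either drug, because nobody chooses the drug for the individual patient. The exclusion list therefore has to carry the contraindications of both. Here it covers allergy to two of the three injected agents (NSAIDs and lidocaine) and omits the third, the corticosteroid.

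Blinding makes the written list matter more than it would in ordinary care. A surgeon who knows that the syringe holds dexamethasone can set that against the patient's allergy and infection history at the moment of injection. In this trial the surgeon does not know what the syringe holds, and the person who does know is not directly involved in the patient's care. The check has to come before randomisation, and the protocol gives no criterion that prompts it.

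What is at stake is the safety of an individual patient with a known hypersensitivity or a systemic fungal infection. Exposure can also be repeated: Section 4.1 allows up to three sites at one visit and two injections per site, and Section 5.5 keeps the patient on the same drug at every site.

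**Working it through.** No formula applies, and the plan gives no figure to reproduce. The check compares the stated contraindications with the eligibility text item by item, then looks for any other step that would catch the same patients.

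**Step 1. Contraindications stated (Sections 1.2 and 5.2.1).** There are two: (a) systemic fungal infection; (b) hypersensitivity to a component of the product, sulfites among them. The steroid allergy in the list of use limitations falls under (b) when the allergy is to dexamethasone itself.

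**Step 2. Compare with Section 4.2.**

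- *(a) Systemic fungal infection.* Not named. The nearest item is the immunocompromised exclusion, which is qualified by HIV/AIDS in brackets. Whether the brackets limit the term or only illustrate it, the item removes some patients at raised risk of such infection. It does not exclude the infection itself.
- *(b) Component hypersensitivity.* Not named. The allergy wording stops at NSAIDs and lidocaine derivatives. The 90-day bullet concerns recent treatment at the site and says nothing about tolerance of steroids.

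Result: of 2 stated contraindications, 0 are named as exclusions, and one of the two is reached in part by another item.

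**Step 3. Look for the items elsewhere.**

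- Section 4.1 (inclusion) covers diagnosis, age, sex, number of sites and injections, splinting, and employees or students. It has no allergy or infection item.
- Section 4.3 (recruitment and screening) describes where patients come from and adds no medical screen.
- Sections 5.1.2 and 5.2.2 (regimens) and 5.7 (concomitant therapy) add none.
- Sections 5.5, 5.6 and 5.8 (assignment, preparation, blinding) describe no check between consent and injection.

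**Step 4. Follow such a patient through the written rules.** The patient meets Section 4.1, triggers nothing in Section 4.2, is enrolled under Section 6, and receives an envelope that may assign dexamethasone. Nothing in these sections stops the injection.

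**Step 5. Is the omission deliberate?** No section argues that steroid or sulfite hypersensitivity, or systemic fungal infection, is acceptable in this trial. The argument that local injection avoids most systemic effects (Section 1.1) is made for NSAIDs, so it does not explain a gap on the steroid side. Section 1.6.1 lists allergic reactions among the risks of ketorolac and of lidocaine but not of dexamethasone. This fits an oversight, though it does not prove one.

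**The case against.** The best reply is that the protocol does not overlook these contraindications: it states them twice, in the document the investigators work from. Dexamethasone is standard of care, and the patients are seen by hand surgeons, who would ordinarily decline to enrol someone with a known steroid allergy. The protocol nowhere directs anyone to treat such a patient. In addition, the Data and Safety Monitoring Plan that Section 8.4 calls attached, and the consent form, are not in the text available here and might contain screening questions.

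Much of this stands, and it limits the weight of the point. Harm would require a known contraindication to be missed or set aside at consent. It does not close the gap, however. Section 6 ties enrolment to the written criteria, and neither unseen document would normally set eligibility. Recruitment also runs through private offices and a resident clinic (Section 4.3), where a written criterion makes practice uniform.

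A reader might infer three stronger claims, none of which the documents support:

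- *That the protocol breaks a commitment to follow the dexamethasone label.* Section 5.2.2 says "Dexamethasone will be used within its labeled indication for this study" and goes on to name the conditions treated. That is a statement about indication and promises nothing about eligibility.
- *That Section 4.2 ignores dexamethasone altogether.* It excludes immunocompromised and pregnant patients, both of whom appear among the use limitations in Section 5.2.1.
- *That ketorolac has the same fault, because nursing and high bleeding risk are not excluded.* Section 5.1.1 ties that list to another use: "In its approved indication it is contraindicated for those with renal impairment, active peptic ulcer disease, pregnant or nursing females". The study use lies outside the approved indication (Section 5.1.2), and Sections 1.1 and 1.6.1 give a reason why not every systemic contraindication need carry over to a local injection. Which ones to keep is a judgement for the investigators.

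**Conclusion.** The point holds in a narrow form. Both contraindications that the protocol states for its comparator are missing from the exclusion criteria, and the enrolment, assignment and blinding procedures as written would let such a patient receive the drug. The missing wording is certain on the text available. How often it would matter is unknown: the documents give no frequency for either condition, so no expected number of patients can be stated, and the equal allocation (Section 7.1: "randomized equally (1:1 randomization") does not supply one.

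This is a minor patient-safety gap that is worth correcting. It should not be read as a threat to the comparison of the two drugs, since no effect on power, bias or any endpoint follows from it. The conclusion rests on two assumptions: that Sections 4.1 and 4.2 hold the complete eligibility criteria, as Section 6 implies, and that no unseen attachment adds to them.

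**What to change.** Add two items to Section 4.2:

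- systemic fungal infection;
- known hypersensitivity to corticosteroids, sulfites or any other component of the dexamethasone product.

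State in Section 5.5 or Section 6 that both are checked before the randomisation envelope is opened, so that every randomised patient can receive either drug.

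The cost is an eligibility amendment, two more lines on the screening checklist, and a few candidates who become ineligible. The sample size, the randomisation method and the analysis stay as they are.
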